## **11.0 Concomitant Medications**

### **11.1 Tapering Instructions**

The site physician will record concomitant medications during Screening. If the prospective participant is being treated with psychiatric medications at enrollment, the prospective participant will be encouraged to discuss medication tapering with their outside treating physician, if any, and will be required to give the site physician permission to do so as well. Additionally, participants who are taking prohibited opiates will be cross-tapered to an allowable opiate (hydrocodone, morphine, and codeine) under the care of their prescribing physician.

The site physician will consult the prescribing physician to initiate medication tapering for participants, as they must refrain from taking psychiatric medications throughout the study, with some exceptions (see [Section 11.2 Allowed Concomitant Medications](#)). The prescribing physician's opinion about medication discontinuation will be documented either in writing from the prescribing physician, or in writing by the site physician documenting phone contact with the prescribing physician. Tapering will follow a time course appropriate for the medication based on its half-life, with the Baseline CAPS-5 T1 (Visit 3) scheduled to occur after complete washout for psychological medications and Experimental Session 1 (Visit 5) scheduled to occur after complete washout for medications with drug-drug interactions without a psychological concern (five half-lives plus at least 1 week for stabilization).

The therapy pair will request information about any changes in medication at each contact. The site physician will be responsible for reviewing and confirming all medications collected during the study.

All medications, non-prescription and prescription, will be collected from Screening through 7 days after the last Experimental Session. From 7 days after the last Experimental Session through Study Termination, only prescription or non-prescription medications taken to treat AEs will be collected. Throughout the protocol, all medications used to treat AEs will be collected, and all changes including discontinuations or additions to medications will be collected. The study team will also inquire about concomitant medication adherence and document all information on the Concomitant Medications eCRF.

Participants may return to taking psychiatric medications and discontinue contraception after the final Study Termination visit if necessary.

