## 3.0 Eligibility Criteria

### 3.1 Inclusion Criteria

At the completion of Screening, participants must meet all eligibility criteria and agree to all lifestyle modifications to be enrolled. Each participant will then enter the Preparatory Period which includes medication tapering, if needed, and non-drug Preparatory Sessions. The Preparatory Period ends with Enrollment Confirmation. A participant's enrollment will be confirmed if they have completed medication tapering, have a confirmed PTSD diagnosis per the CAPS-5 assessment and a Total Severity Score of 28 or greater, a total PCL-5 score of 36 or greater at Screening, continue to agree to all lifestyle modifications, and continue to meet all eligibility criteria (those criteria marked with an \* below will only be assessed at Screening, since they will not change).

Potential participants are eligible to enroll in the protocol if they:

1. \*Are a U.S. military veteran at least 18 years old
2. \*Are able to provide written, informed consent
3. \*Are able to swallow pills
4. Agree to have study visits recorded, including Experimental Sessions, Independent Rater assessments, and non-drug therapy sessions

5. Must provide a contact (relative, spouse, close friend or other support person) who is willing and able to be reached by the investigators in the event of a participant becoming suicidal or unreachable
6. Must agree to inform the investigators within 48 hours of any medical conditions and procedures
7. If able to become pregnant, must have a negative pregnancy test at study entry and prior to each Experimental Session, and must agree to use adequate contraceptive methods through 10 days after the last Experimental Session. Adequate contraceptive methods include intrauterine device (IUD), injected, implanted, intravaginal, or transdermal hormonal methods, abstinence, oral hormones plus a barrier contraception, vasectomized sole partner, or double barrier contraception. Two forms of contraception are required with any barrier method or oral hormones (i.e., condom plus diaphragm, condom or diaphragm plus spermicide, oral hormonal contraceptives plus spermicide or condom). ‘Not able to become pregnant’ is defined as permanent sterilization, postmenopausal, or assigned male at birth

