#### *Initial Eligibility*

Qualified site staff will:

- Review medical and psychiatric history with the participant via interview and review of provided records. If no records were provided or those provided are not sufficient, request additional records. Collect data on previous hospitalizations and healthcare utilization.
- Support the participant during completion of the LEC-5 with PCL-5 to confirm PTSD diagnosis and severity. Support is needed to ensure proper identification of the index trauma on the PCL-5. Symptom severity is assessed in relation to the index trauma.
- Administer the Baseline/Screening C-SSRS to assess history of suicidal behavior and ideation.
- Review past and current medications and adherence to prescriptions.

- Assess ability to become pregnant and discuss requirement for commitment to adequate contraception for the duration of the study. Perform urine pregnancy test for participants who are of able to become pregnant.
- Perform a urine drug test.
- Direct participant to complete self-reported Screening measures:
  - SCID-5-SPQ
  - AUDIT
  - DUDIT
  - PCL-5
  - LEC-5
- Review results of all measures and discussions against eligibility criteria to assess initial eligibility. If deemed initially eligible, potential participant will be provided with instructions (and appointments, if applicable) for a physical exam, laboratory assessments, an electrocardiogram (ECG), and 1-minute rhythm strip. Some or all of these assessments may be at outside facilities.

*Medical Assessments*

The physical exam must be performed by a qualified physician and lab assessments must be completed at a designated lab. Medical assessments will include:

- Blood pressure, pulse, and body temperature measurement.
- Height and weight, which will be used to calculate Body Mass Index (BMI).
- Examination of head, eyes, ears, nose, throat, skin, heart, lungs, abdomen, and extremities.
- Brief neurological exam (cranial nerves 2-12, sensory, motor, reflexes, and cerebellar function).
- ECG and 1-minute rhythm strip.
- Clinical laboratory assessments, per [Section 12.0 Clinical Laboratory Assessments](#). The clinical laboratory values will not be captured in the eCRF but will be used to establish eligibility and will be kept with the participant's source record. Clinically significant abnormal values will be captured as medical history.

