**Table 9: Schedule of Procedures for Experimental Sessions**

Approximate Time	Procedure or Action
8:30	Urine drug screen and pregnancy test, concomitant medication information collected, self-reported measures and C-SSRS administered, participant acclimated to environment
8:55	Baseline BP, body temperature, pulse
9:00	IMP Administration , Begin video recording
10:30	BP, body temperature pulse Supplemental Dose Administration , unless tolerability issues emerge with the first dose or it is refused by the participant
16:30	C-SSRS, BP, body temperature, pulse

*Pre-IMP Administration*

- 24 to 48 hours prior to the first Experimental Session, the participant will be randomized.
- On the day of the Experimental Session, the participant will arrive approximately 30 to 60 minutes prior to IMP administration.
- The therapy pair will direct the participant to complete the PCL-5 and BDI-II and will administer the C-SSRS.
- The site team will ensure the participant has not used caffeine or nicotine 2 hours prior and has fasted for 10 hours prior to IMP administration and complied with all other requirements per [Section 3.3 Lifestyle Modifications](#).
- The site team will inquire about any possible changes in health to ensure the participant continues to meet all eligibility requirements and record AEs as described in [Section 10.0 Safety](#).
- The site team will instruct the participant that they will not be able to use caffeine or nicotine at least 6 hours after the IMP administration.
- The site team will complete urine drug screen, pregnancy test, and concomitant medication review.
  - A positive drug screen will be reviewed by the site physician and may be cause for delaying IMP administration to a later time, rescheduling the session to a later date, or withdrawing the participant from the study, based on Medical Monitor review.
  - A positive pregnancy screen is cause for withdrawal from the protocol.
- The therapy pair will review procedures for the Experimental Session with the participant and discuss the participant's goals, intentions, and concerns and some of the commonly experienced effects of MDMA.
- If the participant continues to be eligible, the session will proceed.
- Baseline blood pressure, body temperature, and pulse will be measured just prior to administration of the initial dose.

*During the Experimental Session*

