People who are able to become pregnant are included in the studies in this program, defined as those who are fertile, following menarche and until becoming post-menopausal unless permanently sterile. Permanent sterilization methods include hysterectomy, bilateral salpingectomy and bilateral oophorectomy. Postmenopausal state is defined as no menses for 12 months without an alternative medical cause. As a precautionary measure in clinical trials, participants who are able to become pregnant must have a negative pregnancy screen before undergoing each Experimental Session, which are conducted in monthly intervals, and must agree to use adequate contraception at least for the duration of the study during the Treatment Period which is 10 days post the last dose of MDMA. The end of relevant systemic exposure to MDMA is approximately 48 hours [117].

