## 10.3 Pregnancy

### 10.3.1 Definition of ‘Able to Become Pregnant’

A participant is considered able to become pregnant if they were assigned female at birth and are post-menarche. A participant is considered not able to become pregnant if they are premenarchal, surgically sterile (documented hysterectomy, bilateral salpingectomy, bilateral oophorectomy, and/or tubal ligation), postmenopausal, or assigned male at birth.

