### 10.3.3 Follow-up Requirements

Details of all pregnancies in study participants will be collected after Enrollment (Visit 0) and collected through 10 days after the last Experimental Session. Pregnancies should be reported to the sponsor via telephone or email within 24 hours of site staff awareness.

In the event of a pregnancy, the participant will discontinue Experimental Sessions but may continue with non-drug Integrative Sessions, the next CAPS-5 assessment, and Study Termination procedures. At a minimum, prior to withdrawal from the study, efforts should be made to assess the final CAPS-5 immediately and complete Study Termination procedures. The participant will be emergency unblinded if the participant wishes as described in [Section 8.4 Blinding and Bias Minimization](#), after the final CAPS-5 assessment.

The investigator will collect follow-up information on the participant and neonate and forward to the sponsor until the outcome of the pregnancy, which will be reported on an optional Pregnancy eCRF. Any termination, elective or spontaneous, will be reported. Abnormal pregnancy outcomes, such as spontaneous abortion, fetal death, stillbirth, congenital abnormalities, or ectopic pregnancy, will be reported as SAEs.

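### The protocol contradicts itself on when contraception may end, whether tubal ligation counts as sterile, and whether a positive pregnancy test ends participation or only dosing

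*Protocol*

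**What the plan says.** **End of contraception.** Under Protocol 3.1, criterion 7, a participant able to become pregnant "must agree to use adequate contraceptive methods through 10 days after the last Experimental Session". In Section 7.1.1, screening staff are to "discuss requirement for commitment to adequate contraception for the duration of the study". Section 9.2.3.4 runs the two ideas together: "duration of the study during the Treatment Period which is 10 days post the last dose of MDMA". Section 11.1 states: "Participants may return to taking psychiatric medications and discontinue contraception after the final Study Termination visit if necessary".

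**Sterility.** Section 10.3.1, which defines who is able to become pregnant, excludes those who are "surgically sterile (documented hysterectomy, bilateral salpingectomy, bilateral oophorectomy, and/or tubal ligation". Section 9.2.3.4 reads: "Permanent sterilization methods include hysterectomy, bilateral salpingectomy and bilateral oophorectomy". Criterion 7 refers to permanent sterilization and names no procedure.

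**Positive test.** The pre-dose instructions in Section 7.3.1 (below Table 9) say: "A positive pregnancy screen is cause for withdrawal from the protocol". Section 10.3.3 says that after a pregnancy "the participant will discontinue Experimental Sessions but may continue with non-drug Integrative Sessions", and extends this to the next CAPS-5 and the Study Termination procedures. Section 4.4.3 names pregnancy among the events that stop Experimental Sessions while the participant stays in the study for the related Integrative Sessions.

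**The concern.** Each of these rules is applied by site staff to an individual participant, and each has a different answer in different sections. A participant can be given one contraception end date from the eligibility criteria and another from the medication section. A participant with a tubal ligation may or may not be tested before receiving MDMA. A participant with a positive test may be taken off the protocol or kept in follow-up.

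Two consequences are statistical. The SAP's introduction moves the focus of the analysis to safety, and it is the later safety contacts of an exposed participant that depend on which section is followed. SAP 7.3 also grades protocol deviations as major or minor. Where two sections disagree, the same conduct complies with one and breaches the other, so the grading has no fixed reference.

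**Working it through.** The plan states no figure for the contraception gap, so there is none to reproduce. The gap follows from the protocol's own windows; the other two conflicts are comparisons of text.

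**1. Gap between the two contraception end dates**

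Inputs:
- T2 falls 49 to 56 days after the last Experimental Session (Table 1).
- T2.2, 2-session group only, falls 28 to 35 days after T2 (Table 1).
- Study Termination falls 1 to 7 days after the final CAPS-5 (Section 7.4.2; Table 6 agrees for the 2-session group).
- In the 3-session group, Table 5 instead chains V18 at 1 to 7 days after T2 and V19 at 0 to 7 days after V18.
- Criterion 7 ends contraception at day 10 after the last session.

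Study Termination day = sum of the windows from the last session. Gap = that day − 10.

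| Group and source | Study Termination, days after last session | Gap, days |
|---|---|---|
| 3-session, Section 7.4.2 | 49 + 1 = 50 to 56 + 7 = 63 | 40 to 53 |
| 3-session, Table 5 | 49 + 1 + 0 = 50 to 56 + 7 + 7 = 70 | 40 to 60 |
| 2-session | 49 + 28 + 1 = 78 to 56 + 35 + 7 = 98 | 68 to 88 |

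The upper limit for the 3-session group depends on whether Section 7.4.2 or Table 5 governs the termination visit.

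**2. Who is tested**

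The footnotes to Tables 4 to 6 restrict the pregnancy screen to people able to become pregnant. Sections 10.3.1 and 9.2.3.4 share three procedures (hysterectomy, bilateral salpingectomy, bilateral oophorectomy) and differ by one, tubal ligation. Under 10.3.1 a participant with a documented tubal ligation is outside the tested group. Under the list in 9.2.3.4 the same participant is not shown to be outside it. Criterion 7, which sets eligibility, does not decide the matter.

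**3. What a positive test leads to**

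| Section | Dosing | Participation afterwards |
|---|---|---|
| 7.3.1 | Ends | Grounds for withdrawal from the protocol |
| 4.4.3 | Ends | Stays for the associated Integrative Sessions |
| 10.3.3 | Ends | May continue Integrative Sessions, next CAPS-5 and Study Termination procedures |

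All three end dosing. They differ on what follows.

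For withdrawal, Section 10.3.3 asks at least for efforts to obtain a final CAPS-5 at once and to complete the Study Termination procedures, which under Section 7.4.2 include AE review and the C-SSRS. It also follows the pregnancy to its outcome. Sessions are 21 to 35 days apart, so a CAPS-5 taken at a positive test before Session 2 or 3 would come 21 to 35 days after the previous dose, against 49 to 56 days for T2. What a withdrawal under 7.3.1 puts at risk is therefore the T2 assessment on its schedule and the AE and C-SSRS contacts that would have followed.

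**The case against.** The strongest reply is that most of this is settled by reading the sections together. Section 9.2.3.4 ties study duration to 10 days after the last dose, so Section 7.1.1 can be read as agreeing with criterion 7. That leaves 11.1 as the one outlier, a permissive sentence in a section on tapering. The sterility list in 9.2.3.4 is introduced as inclusive and sits in a risk narrative about the wider program, whereas 10.3.1 is the titled definition. Section 10.3.3 is the dedicated pregnancy section, foresees withdrawal, and says the participant may continue, not must. The study has also stopped at about 20 participants, with descriptive efficacy only.

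Much of this stands. The link in 9.2.3.4 does soften the conflict with 7.1.1, but leave to stop contraception after Study Termination implies no leave before it, so 11.1 and criterion 7 still disagree. An inclusive reading of 9.2.3.4 removes the direct contradiction but does not settle tubal ligation in that section or in criterion 7. Section 7.3.1 is the session-day instruction and carries no cross-reference to 10.3.3.

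A reader might infer that a pregnant, exposed participant's AE, C-SSRS and CAPS-5 data are all lost under 7.3.1. The text does not support that: Section 10.3.3 asks for an immediate CAPS-5 and the termination procedures, and Section 4.4.3 has the site seek AE outcomes after early termination where appropriate. A positive test before Session 1 concerns someone not yet dosed in the study. Nor does the pregnancy sentence in 4.4.3 promise further CAPS-5 assessments; it names Integrative Sessions only.

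**Conclusion.** The protocol is inconsistent on three operative points: the contraception end date, the status of tubal ligation, and participation after a positive pre-session test. The end dates differ by 40 to 53 days in the 3-session group (up to 60 by Table 5) and by 68 to 88 days in the 2-session group, assuming visits fall within their windows and all assigned sessions are given.

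A reader might also infer that the timing of pregnancy testing depends on the section. It does not. Criterion 7 and Tables 4 to 6 agree on testing at entry and before each Experimental Session, and Section 10.3.3 gives a single end date for collecting pregnancies. Only who is tested is in doubt.

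The documents do not say how many participants are able to become pregnant or have had a tubal ligation, so the number affected cannot be estimated. With the primary efficacy analysis dropped (SAP 6.0 and 7.7.1), no planned inference depends on this. The conflicts bear on participant instructions, pre-dose testing, completeness of safety follow-up and the grading of deviations. They are worth correcting on those grounds.

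**What to change.** The passages must be reconciled; which clinical rule applies is for the sponsor to decide.

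- State one contraception end date in criterion 7 of 3.1 and in 7.1.1, 9.2.3.4 and 11.1.
- State one definition of sterility in criterion 7, 9.2.3.4 and 10.3.1, saying explicitly how tubal ligation is treated.
- State one consequence of a positive test in 4.4.3, 7.3.1 and 10.3.3.
- In 7.3.1, distinguish stopping Experimental Sessions from ending data collection and cross-refer to 10.3.3, so that a dosed participant who has not withdrawn consent is still followed for AEs, C-SSRS and CAPS-5.

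The same edit could reconcile a related conflict: criterion 7 lists abstinence among the adequate methods, whereas 10.3.2 does not accept it on its own.

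The cost is a protocol clarification, with no new visit, test or procedure. Where conduct has already followed one of the conflicting sections, record the rule applied when grading deviations under SAP 7.3.

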## 11.2 Allowed Concomitant Medications

The site physician may prescribe necessary and appropriate medications in accordance with local and state regulations during the study to treat AEs that do not respond to other management outlined in the Treatment Manual. Examples include concomitant benzodiazepines for uncontrolled anxiety (for example, lorazepam at modest doses and occasional use only to avoid withdrawal effects of discontinuation between Experimental Sessions) or sleep aids (excluding trazodone) in compliance with [Section 11.3 Prohibited Medications](#).

Gabapentin or certain opiates will be allowed when prescribed for pain management. The following opiates will be allowed during the study: hydrocodone, morphine, and codeine. Prior to randomization, participants who are taking opiates not included on this list will be cross-tapered to an allowable opiate under the care of their prescribing physician. Opiate medications may reduce the efficacy of MDMA and may prolong QT/QTc interval, but the opiates that are allowed during this trial have been selected because they have the lowest potential for QT/QTc interval prolongation. Individuals using opiates for pain management will be asked to decrease the dose leading up to the Experimental Session in order to avoid withdrawal effects when they are required to refrain from taking the medication from 12 hours before IMP administration at the Experimental Session to 24 hours after. During this period, the participant will be allowed to take the medication if needed for intolerable pain flare-ups or to prevent withdrawal symptoms. If a participant reports lack of analgesic effect during the sub-acute period following each Experimental Session, the site physician may approve taking an allowed opiate medication sooner than 24 hours after IMP administration.

If the participant is on stimulants for Attention Deficit/Hyperactivity Disorder (ADHD) at Baseline, they can continue to use them at the same dose and frequency, as long as they discontinue five half-lives before each Experimental Session and do not restart for 10 days after each Experimental Session.

All psychoactive medications, herbal supplements, nonprescription medications, and prescription medications must be reviewed by the research team. Failure to comply with protocol requirements for concomitant medications may result in withdrawal from treatment, depending on the investigator and Medical Monitor judgment.

## 11.3 Prohibited Medications

To be enrolled in the study, participants must:

- Refrain from the use of any psychoactive medication not approved by the research team from Baseline through Study Termination (with the exception of gabapentin or certain opiates for pain control).
- Be willing to comply with all medication requirements per protocol. Medications will only be discontinued after enrollment per clinical judgment of the site physician in consultation with the prescribing physician.
- Agree that, for 1 week preceding each Experimental Session they will refrain from:
  - Taking any specified herbal supplement (except with prior approval of the research team).
- Agree that, for 5 half-lives of the medication preceding each Experimental Session they will refrain from:

- Taking any nonprescription medications (with the exception of non-steroidal anti-inflammatory medications or acetaminophen) unless with prior approval of the research team.
- Taking any prescription medications (with the exception of birth control pills, thyroid hormones, or other medications approved by the research team).

Use of Marijuana, St. John's Wort, and other herbs and medicines with notable serotonergic effects are prohibited from Baseline to Study Termination. Any investigational treatments under study for PTSD treatment are prohibited from use concurrent with this study.

Diphenhydramine is excluded from this study unless prior approval is granted by the site physician.

If an SSRI, SNRI, MAOI, or other antidepressant is used between Experimental Session 1 (Visit 5) and Study Termination, the participant will be withdrawn from treatment and continue in follow-up.

Opiates other than hydrocodone, morphine, and codeine are prohibited from Enrollment Confirmation to Study Termination. Participants taking prohibited opiates will be cross-tapered to an allowable opiate during the Preparatory Period. Participants whose Experimental Sessions are delayed by the COVID-19 pandemic may start any of these medications during the delay, as clinically indicated. When study visits resume, they will be given the option to resume Experimental Sessions after tapering off of these medications, per the tapering plan described above.

